5.2.6 Additional Warnings and Precautions

CDX-301

Drug-drug Interactions

Interactions between CDX-301 and other drugs have not been fully evaluated.

Allergic Reaction

CDX-301 is a fully human protein, and it is unlikely that it will induce a hypersensitivity reaction. No such reactions have been observed in the CDX-301 programs to date; nor were any such reactions reported in the AMG949 clinical development program. If such reactions were to be observed, possible manifestations could include fever, chills, rash, rigors, pruritus, or other symptoms.

Immunogenicity

None of the 30 healthy volunteers treated in the Phase I trial with CDX-301 (5 to 10-day regimen) developed anti-rhuFlt3L antibody. In the Celldex-sponsored pilot study, CDX301-03, none of the four donors administered CDX-301 had detectable anti-rhuFLT3L antibodies at any collection time point.

The immunogenicity of CDX-301 has also been investigated in two investigator-sponsored studies. In CDX301-51, the effects of intratumoral injection of CDX-301 and poly-ICLC were studied in low grade B-cell lymphoma. Samples were collected from 15 patients for anti-CDX-301 immunogenicity testing. One patient has been found positive for anti-CDX-301 immunoreactivity. To date, no neutralizing responses have been observed. Immunogenicity samples were collected from 30 patients in CITN-07 (CDX1401-54). Of the 144 total samples collected, none were found to exhibit a specific anti-CDX-301 response.

Approximately 16% of subjects treated with AMG949 in Immunex sponsored studies and tested for immune response were noted to develop anti-rhuFlt3L antibody. Anti-rhuFlt3L antibodies appeared to develop more frequently in studies with greater exposure to AMG949. However, none of the anti-rhuFlt3L antibodies were neutralizing.

In theory, neutralizing antibodies could develop following administration of CDX-301, with potential consequences of neutralizing subsequent CDX-301 effects, neutralization of endogenous Flt3L activity that could result in bone marrow suppression, inhibition or enhancement of immune responses, and/or result in immune complex mediated disease. Although this scenario is considered extremely unlikely to occur with CDX-301, patients will continue to be monitored for anti-CDX-301 antibodies and whether these antibodies are neutralizing.

Coagulation

No thrombotic events have been reported as potentially related to CDX-301 in the Celldex clinical development program to date. Thrombotic events (hypercoagulability, IV line thrombosis, and venous thrombosis) were observed rarely in oncology patients (n = 6) receiving AMG949 and was more common when combined with GM-CSF or G-CSF. Low grade thrombocytopenia has also been observed following AMG949 administration. Evaluation of coagulation parameters and clotting factors in several of these patients did not reveal any abnormalities.

Autoimmune Disease

Subjects with a known history of autoimmune disorders should not be given CDX-301, until further studies have determined the safety profile of CDX-301 in this patient population. Pre-clinical studies have demonstrated that rhuFlt3L may have a complicated role in regulating autoimmune diseases and can either exacerbate or ameliorate autoimmune disease manifestations. Therefore, CDX-301 may have the potential to exacerbate autoimmune disorders by its immunomodulatory effects.

Subjects administered CDX-301 will be monitored for the development of potential autoimmune phenomena, such as hyper- or hypothyroidism.

Development of Immune Tolerance

CDX-301-mediated increases in immature dendritic cells and/or Treg cells could potentially be tolerogenic. Therefore, CDX-301 could potentially have deleterious effects in an infectious disease setting or other pre-existing or developing disease. AMG949 worsened the outcome in a mouse *Streptococcus pneumoniae* pneumonia challenge model⁹⁵, indicating that rhuFlt3L treatment could pose a risk for increased lung injury associated with *S pneumoniae* pneumonia. Study subjects should be monitored for the development of infections conditions.

rhuFlt3L may also be associated with a differential response to vaccines. In another murine model, intramuscular injection of rhuFlt3L in combination with a hepatitis B vaccine suppressed the antibody response to the vaccine in a dose-dependent manner, although *in situ* delivery by plasmid increased the antibody response⁹⁶. In a clinical study in which healthy volunteers were administered hepatitis B vaccine and either placebo or AMG949, there was no inter-group difference in hepatitis B antibody responses, demonstrating that AMG949 neither augmented or tolerized humoral responses to the vaccine.

Leukemia

There are data showing that prophylactic treatment with rhuFlt3L can prevent or abrogate leukemic activity⁹⁷. There also are data showing the expression of Flt3 and the Flt3L receptor, on some leukemias, and extensive data that support an association between an increase in proliferation or suppression of apoptosis in clinical leukemias that bear constitutively activated Flt3 mutations. These mutations do not appear to be causal for AML⁹⁸⁻¹⁰¹. It is not known whether the addition of rhuFlt3L to patients with leukemia expressing Flt3 will promote leukemic proliferation, or whether the ligand can promote the development of leukemia in people without pre-existing leukemia. Since the effect of administered rhuFlt3L is transient, it would seem unlikely to have any persistent effects and no cases of leukemia were reported after rhuFlt3L administration in previous studies.

Pregnancy, Carcinogenesis, and Teratogenicity

The effects of CDX-301 on fertility, pregnancy, or the unborn fetus have not been determined. It is not known if CDX-301 is excreted in milk or can cross the placenta. For this reason, pregnant and nursing women should not receive CDX-301. Women of childbearing potential treated with CDX-301 must take adequate contraceptive measures.

CDX-1140

Most side effects associated with CDX-1140 to date have occurred in the 24-48 hours following the CDX-1140 infusion, been mild to moderate, and have resolved with or without medications such as acetaminophen, NSAIDS, and/or anti-nausea medication. In a few cases, the side effects have been severe and have required hospitalization and treatment with corticosteroids or other immunosuppressive medications. Treatment related adverse events that have occurred in > 10% of patients include fatigue, arthralgia, nausea, chills, fever, diarrhea, myalgia, vomiting, AST increase, and ALT increase.

Cytokine Release Syndrome

2 patients who received CDX-1140 monotherapy and 4 patients who received CDX-1140 in combination with CDX-301 have experienced cytokine release syndrome. Symptoms included fever, hypotension, hypoxia, fatigue, headache, and nausea.

Pneumonitis

4 patients who received CDX-1140 monotherapy experienced severe treatment-related pneumonitis, with 3 of the 4 developing pneumonitis during the first week of treatment. These patients developed shortness of breath, and imaging of the lungs demonstrated new inflammatory changes. Two patients required intubation. All four patients were treated with high dose corticosteroids, and two of the patients subsequently died, due to a documented infection in one patient and presumed infection in the other. Two patients demonstrated clinical improvement temporally associated with the administration of tocilizumab. Of note, tocilizumab has not been incorporated into the treatment guidelines for management of pneumonitis associated with immune checkpoint blockade therapy,¹⁰² but there is a case series suggesting that tocilizumab is effective in the management of corticosteroid-refractory pneumonitis irAEs¹⁰³. Based on the rapid response temporally associated with the administration of tocilizumab in the cases discussed above, and the case series suggesting that tocilizumab may be beneficial in treating checkpoint-related pneumonitis, tocilizumab should be considered as a therapeutic option in those patients with CDX-1140 related, steroid-refractory pneumonitis, as well as for other high grade steroid-refractory adverse events.

Thrombosis

CD40 is functionally expressed on platelets and endothelial cells, and CD40 signaling could theoretically promote a pro-thrombotic state. In the CDX1140-01 study, 1 patient developed a deep vein thrombosis and pulmonary embolism that was considered related to CDX-1140. Administration of CP-870,893, another agonist anti-CD40 mAb, was associated with transient increases in D-dimer and thrombin-antithrombin 3 complex formation levels at the 2 highest doses tested (0.2 and 0.3 mg/kg) in the Phase 1 study⁶³. Standard coagulation parameters were not affected by CP-870,893. One patient with a prior history of deep vein thrombosis had a drug-related thromboembolic dose-limiting toxicity.

Elevated liver enzymes

Increases in liver function tests in the 24-48 hours following the CDX-1140 are an expected pharmacodynamic effect of the drug. The increases are usually low-grade, but can be grade 3, and liver function tests typically return to approach baseline within a week. Treatment of these transient changes is not indicated. More significant changes in laboratory tests may be followed more closely, if clinically warranted, and may require intervention per irAE guidelines^{102,104} if the changes are associated with clinical symptoms or persistent

Decreased lymphocyte and monocyte counts

Decreases in lymphocyte and monocyte counts are a pharmacodynamic effect of CDX-1140, occurring within 24-48 hours of a dose and typically recovering by 1 week. Decreases in B cells, as determined by flow cytometry, predominates.

Other Adverse Events

Based on a review of the relevant literature and the proposed mechanism of action of CDX-1140 in binding to CD40 expressing cells and enhancing immune reactions, the following additional adverse effects may be encountered:

- Infusion reactions/cytokine release syndrome/hypersensitivity reactions
 - As mentioned above, infusion reactions are likely to occur and may include chills, rigors, fever, rash, nausea, vomiting, myalgias, headache, and hypotension. Obtain serum at the time of an infusion reaction/cytokine release syndrome.
 - As discussed above, patients are to be pre-medicated with antihistamine, acetaminophen, and/or NSAID at least 30 minutes prior to CDX-1140 administrations. Prophylactic premedication with corticosteroids is to be avoided with CDX-1140 because of the potential to attenuate antitumor activity. In the 24 hours following the CDX-1140 infusion, alternate oral acetaminophen (1000 mg) and non-steroidal anti-inflammatory (e.g., ibuprofen 200 mg) q6h. An antihistamine and anti-emetic may also be utilized if clinically indicated.
- Immune-related adverse events (irAEs)
 - An irAE is defined as a clinically significant adverse event of any organ that is associated with study drug exposure, of unknown etiology, and is consistent with an immune-mediated mechanism. Serologic, immunologic, and histologic (biopsy) data should be used to support an irAE diagnosis. Appropriate efforts should be made to rule out neoplastic, infectious, metabolic, toxin, or other etiologic causes of the adverse event. Most commonly irAEs involve skin, gastrointestinal (GI) tract, endocrine organs and liver, but can involve any organ system. irAEs typically clinically manifest several weeks to a few months following initiation of immune enhancing anti-tumor therapy. Possible clinical manifestations include:
 - Constitutional: fever, fatigue
 - GI: diarrhea, colitis, constipation, hematochezia, melena, abdominal pain, pancreatitis
 - Skin: rash, pruritus, alopecia, desquamation
 - Liver: elevated liver enzymes, hepatitis

- Endocrine: hypothyroidism, hyperthyroidism, adrenal insufficiency, hypophysitis, hypogonadism, diabetes
- Ocular: conjunctivitis, iritis, uveitis
- Others: neuropathy, including Guillain-Barre syndrome, hemolytic anemia, thrombocytopenia, pneumonitis

Guidelines have been published for the management of irAEs associated with immunotherapy,^{102,104,105} and investigators should be familiar with the workup and treatment of irAEs. Obtain serum at the time of any \geq Grade 3 suspected drug related irAE.

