3.2 Exclusion Criteria

- Prior therapy with any anti-CD40 antibody or FLT3 ligand
- Less than 21 days between planned study treatment start and the last receipt of chemotherapy, targeted cancer therapy, immunotherapy, radiotherapy (excluding palliative radiotherapy), or major surgery.
- Untreated central nervous system metastases. Patients with a history of brain metastases must have had no CNS-directed therapy within the past 60 days and radiological assessment within 30 days of study entry demonstrating a lack of progressive CNS disease. Patients without a history of brain metastases and without symptoms suggestive of brain metastasis do not require staging imaging of the brain prior to study enrollment.
- Known mutation/amplification in FLT3
- Ongoing use of high dose oral corticosteroids (\geq 2 mg of dexamethasone daily or equivalent) or inhaled corticosteroids. Intranasal and/or intraarticular corticosteroid use is permitted.

- History of non-infectious pneumonitis or any ongoing pneumonitis
- History of allogeneic organ transplant or active autoimmune disease
- Other active malignancy for which systemic therapy (excluding hormonal therapy for breast or prostate cancer) is indicated.
- History of myocardial infarction, cerebral vascular accident, thrombosis, or pulmonary embolus within 12 months prior to study registration.
- Uncontrolled intercurrent illness including, but not limited to, symptomatic congestive heart failure, unstable angina pectoris, uncontrolled cardiac arrhythmia, or psychiatric illness/social situation that would limit compliance with study requirements as judged by the treating physicians
- Active infection requiring systemic therapy, known HIV infection, or positive test for hepatitis B surface antigen or hepatitis C (antibody screen and if positive confirmed by RNA analysis). If positive results are not indicative of a true active or chronic infection, the patient can be enrolled after discussion with, and agreement by, the Principal Investigator.

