4.1 General Design

This is a randomized, open-label phase I/II study. Subjects will be randomized in a 1:1 ratio to receive FLT3 ligand, anti-CD40 antibody, and SBRT (Arm 1) versus standard care (Arm 2). Subjects on either study arm with limited disease will receive SBRT to all evident sites of active disease. Subjects on Arm 1 with extensive disease will initially receive SBRT to a single site of disease but may receive additional “cycles” of FLT3 ligand, anti-CD40 antibody, and SBRT at later time points. Subjects on Arm 2 with extensive disease are expected to receive some form of standard systemic therapy (e.g., docetaxel). Subjects on Arm 2 with limited disease may also receive standard systemic therapy following completion of SBRT to all sites of evident disease, at the discretion of the treating physicians. All subjects will be followed closely for treatment-related toxicities. Whole-body PET/CT and CT imaging will be performed prior to study entry, and restaging CT will be performed every 8 weeks thereafter.

In the phase I component of this study, subjects will be randomized between study arms until 6 subjects have been randomized to Arm 1. Study accrual will then be halted until 8 weeks after the last study subject begins treatment.

If the pre-specified safety criteria are achieved in the Phase I portion of this study, the study will proceed to phase II. The total sample size (Phase I and Phase II) will be 46 subjects. All 46 subjects will be included in efficacy analyses.

If the pre-specified safety criteria are not achieved in the Phase I portion of this study, the investigators and Celldex will review safety data from this trial as well as other trials using CDX-301 and CDX-1140 and determine if the experimental treatment regimen should be altered (e.g., by reducing the CDX-1140 dose). The study protocol would be amended accordingly, and Phase I component with the new treatment regimen would be added.

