4.2.2 Arm 1 (experimental study arm)

ARM 1	Week 1	Week 2	Week 4	Week 6	Weeks 9 ¹ , 17 ² , 25 ² , 33 ² , 41 ² , 49 ²
History and Physical Examination	X	X ⁵ X ⁶	X	X ⁵ X ⁶	X
CBC, BMP, LFTs, Amylase, Lipase	X	X ⁵ X ⁶	X	X ⁵ X ⁶	X
Activity Data Download ³	X	X	X	X	X
QoL Assessments		X	X	X	X
Correlative Study Blood Draw		X ⁷		X ⁷	X
CDX-301 ADA and CDX-1140 PK		X ⁷ X ⁸ X ⁶		X ⁷ X ⁶	
CT C/A/P					X
Stereotactic Radiotherapy (SBRT) ⁴	XXX				
FLT3 Ligand (CDX-301)	XXXXX				
CD40 Agonist Antibody (CDX-1140)		X		X	

1. +/- 1 week

2. +/- 2 weeks

3. For subjects who opt to participate in this part of the study

4. SBRT should be delivered in 1, 3, or 5 fractions per target and may continue beyond Week 1 when treating multiple sites.

5. On the day of CDX-1140 infusion

6. One day after CDX-1140 infusion

7. Immediately before CDX-1140 infusion

8. 2 hours after CDX-1140 infusion

Cycles of SBRT(to an untreated lesion)+CDX-301+CDX-1140 may be repeated.

- At least 8 weeks must separate the start of each treatment cycle.
- CDX-1140 may be omitted from retreatment cycles for subjects with prior DLT or intolerable toxicity attributed to CDX-1140.
- The schedule of assessments will reset when a new cycle is initiated.

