5.2.2 Treatment Schedule

CDX-301 and CDX-1140 will only be administered to subjects on Arm 1. Subjects on Arm 2 will not “crossover” if disease progression is observed. The Study Calendar (Section 4.2) describes the timing of study drug administrations.

Some subjects on Arm 1 may receive more than one “cycle” of CDX-301, CDX-1140, and SBRT (targeting a lesion not previously treated with SBRT). The decision to administer treatment cycles beyond cycle 1 must be agreed upon by the treating physicians, the principal investigators, and the study subject. Additional treatment cycles will not be offered to subjects who develop disease progression within four months of receiving a previous cycle of study therapy or to subjects who have no evidence of active disease. Subjects who previously experienced DLT or intolerable toxicity related to CDX-1140 may be treated with CDX-301 and SBRT and without CDX-1140 in subsequent treatment cycles.

For subjects who receive more than one cycle of study therapy, the schedule of events will reset at the beginning of each cycle. At least 8 weeks must separate the start of each treatment cycle.

CDX-301

Five injections of CDX-301 should be administered daily during Week 1 (Monday-Friday) of a treatment cycle. If that is not possible due to department closure for a national holiday, inclement weather, or another reason that is not treatment-related toxicity, CDX-301 treatment may extend to Week 2 (though not beyond 10 days after the first CDX-301 dose).

CDX-1140

The first CDX-1140 will take place 4 days (+/- 1 day) after the last dose of CDX-301. As CDX-301 will typically be given from Monday-Friday, CDX-1140 will usually be given on a Tuesday. The second dose of CDX-1140 will be given 4 weeks (+/- 3 days) after the first CDX-1140 dose. CDX-1140 will not be administered on a Friday, as a clinic visit the day after each CDX-1140 dose is required.

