5.2.4 Potential Toxicities and Toxicity Management

Potential toxicity and guidance for the management of toxicity is summarized below. However, the CDX-1140 and CDX-301 Investigator Brochures (IB) are the Single Reference Safety Documents that provide complete and relevant information about the known safety profile of CDX-1140 and CDX-301.

CDX-301

CDX-301 was generally well-tolerated in all prior studies, including our prior study of CDX-301 and SBRT for advanced NSCLC, which utilized the same CDX-301 dose/schedule as the present trial. The most frequently observed toxicities related to CDX-301 have been asymptomatic lymphadenopathy and mild injection site reactions.

Injection site reactions have been infrequent and mild with CDX-301. No injection site reactions were observed in our recent trial combining CDX-301 and SBRT (29 subjects, 180 injections). Generally mild to moderate injection site reactions were reported in studies using AMG949. Pre-medication with diphenhydramine has been reported to be effective in the prevention of pruritic and erythemic reactions⁹³ and may be considered for subjects who experience local reactions after treatment with CDX-301. Injection site reactions may also be treated with analgesics (i.e., Tylenol). If there is injection site pain, a numbing cream such as Emla cream can be used prior to administration of CDX-301. Patients will be monitored for 30 minutes following each CDX-301 injection.

Leukocytosis, especially monocytosis, is expected during administration of CDX-301. Hematological parameters, including WBC and differential, should be monitored in subjects receiving CDX-301. CDX-301 should not be administered if marked leukocytosis, e.g. WBCs greater than 50,000 cells/mm³, is observed.

CDX-1140

The CDX1140-01 study was the first clinical trial with CDX-1140, and therefore there is limited clinical experience to define expected toxicities. Management of drug-related adverse events and serious adverse events should be in accordance with the institution's standard of care and guidelines for managing immune related toxicities⁹⁴.

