5.2.5 Dose Modifications

CDX-301

There will be no CDX-301 dose modifications. If discontinued, CDX-301 will not be reinstated. CDX-301 should not be administered if marked leukocytosis, e.g., WBCs greater than 50,000 cells/mm³, is observed. Any \geq Grade 3 injection site reactions thought related to CDX-301 warrant discontinuation of CDX-301 treatment and will be considered a DLT. If CDX-301 is discontinued due to a DLT, treatment with CDX-1140 may continue in the absence of a CDX-1140-related DLT.

CDX-1140

CDX-1140 dose modifications are not allowed. The second CDX-1140 infusion should only be administered if the subject is receiving \leq 10 mg/day prednisone or equivalent for treatment of drug related toxicity, and all toxicity related to prior treatment (including laboratory abnormalities) has resolved to \leq grade 1, with the following exceptions:

- Subjects may receive treatment in the presence of grade 2 fatigue
- Subjects who have not experienced a grade 3 drug-related skin AE may receive treatment in the presence of grade ≤ 2 skin toxicity
- Subjects with baseline grade 1 AST/ALT or total bilirubin elevation may receive treatment in the presence of grade 2 AST/ALT or total bilirubin elevation
- Grade 2 drug-related pulmonary toxicity, diarrhea, or colitis, must have resolved to baseline before treatment is received
- Patients with drug-related endocrinopathies adequately controlled with only physiologic hormone replacement may receive treatment
- Asymptomatic lymphopenia
- Clinically asymptomatic increased amylase or lipase. The medical monitor should be consulted in the event of grade 4 elevations in amylase or lipase.

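### The eligibility list, on its more natural reading, excludes only active autoimmune disease, but Section 5.2.6 says patients with any known history should not receive CDX-301, so a patient the drug precaution rules out can be randomised to Arm 1

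*Combined protocol and SAP*

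**What the plan says.** Two places in the combined protocol and SAP deal with pre-existing autoimmune disease.

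- **Section 3.2 (Exclusion Criteria)** lists "History of allogeneic organ transplant or active autoimmune disease". No other item in Sections 3.1 or 3.2 mentions autoimmune disease.
- **Section 5.2.6 (Additional Warnings and Precautions, CDX-301)** says "Subjects with a known history of autoimmune disorders should not be given CDX-301", and keeps that restriction in place until the drug's safety in this population has been studied. It does not limit the restriction to active disease. The reason given is that "CDX-301 may have the potential to exacerbate autoimmune disorders by its immunomodulatory effects". The same paragraph provides for monitoring treated subjects for new autoimmune phenomena.

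Section 8.1 places stratification and 1:1 randomisation at registration. Sections 4.1, 4.2.2 and 5.2.2 make CDX-301 part of Arm 1 treatment, as five daily injections in Week 1.

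On leaving out a study drug, Section 5.2.5 says "If CDX-301 is discontinued due to a DLT, treatment with CDX-1140 may continue in the absence of a CDX-1140-related DLT". Section 4.2.2 says "CDX-1140 may be omitted from retreatment cycles for subjects with prior DLT or intolerable toxicity attributed to CDX-1140", and Section 5.2.2 repeats that in substance.

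**The concern.** The group described in Section 5.2.6 is wider than the group removed by Section 3.2. The difference is patients whose autoimmune disease is in the past or inactive. They can pass the eligibility list, be registered and be allocated to Arm 1.

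One of two things then happens. The subject may receive CDX-301 although the protocol says people with that history should not. Or someone notices the precaution after allocation and withholds CDX-301 from the first dose, and the site must decide for itself what the subject's Arm 1 treatment now is. Safety is at stake in the first case. In the second, the subject's treatment departs from the randomised regimen with no stated rule behind it. A screening question asked before allocation would prevent both.

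**Working it through.** The protocol states no figure on this point, so the check is a comparison of texts.

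**Step 1: who is excluded.** The Section 3.2 bullet can be read in two ways.

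| Reading of the bullet | Past or inactive disease | Agreement with Section 5.2.6 |
|---|---|---|
| History of transplant, or autoimmune disease that is active now | Eligible | Conflict |
| History of transplant, or history of autoimmune disease that was once active | Mostly excluded | Largely agrees, though the wording still differs |

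The first reading is the more natural. The word *active* adds little if *history of* already governs the phrase. The neighbouring pneumonitis criterion also shows how this list covers both past and current disease: it names each separately. The autoimmune bullet does not.

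**Step 2: whether another criterion closes the gap.** None of the remaining items in Sections 3.1 and 3.2 refers to autoimmune disease. The corticosteroid exclusion would catch some patients on current treatment, but not someone with quiescent disease and no steroid use.

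**Step 3: whether such a patient can reach Arm 1.** Randomisation takes place at registration in a 1:1 ratio, and the strata are EGFR/ALK status and disease burden. Autoimmune history plays no part. For each such patient registered, the probability of Arm 1 is 1/(1 + 1) = 1/2.

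**Step 4: what the protocol says next.**

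| Provision | Covers | Applies to a contraindication known at baseline? |
|---|---|---|
| Section 5.2.6 | Do not give CDX-301 | Yes, but does not say what to give instead |
| Section 5.2.5 | CDX-1140 may continue after CDX-301 is stopped for a DLT | No, since nothing was started and no DLT occurred |
| Sections 4.2.2 and 5.2.2 | CDX-1140 may be left out of later cycles | No, it concerns the other drug and retreatment |

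The timing of CDX-1140 is not the difficulty. Section 5.2.2 counts the first infusion from the last CDX-301 dose, but it also says "The Study Calendar (Section 4.2) describes the timing of study drug administrations", and that calendar puts the infusions in Weeks 2 and 6. What is missing is a statement that SBRT plus CDX-1140 alone is, or is not, the intended treatment for a subject who should never start CDX-301.

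**Step 5: how often.** The documents give no prevalence of past or inactive autoimmune disease in this population, so no probability of occurrence can be derived from them.

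**The case against.** The strongest reply is that the two sections do not contradict each other. Section 3.2 says who may not enrol; Section 5.2.6 says who should not be dosed. An investigator can obey both by not registering the patient, and Section 9.2 requires the study to be run as the protocol describes. That is correct, and it means dosing against the precaution requires someone to overlook protocol text. But the eligibility list is where the question should be asked, and it does not ask it. The precaution sits in a drug section that bears on only one arm, and allocation has happened by the time it applies.

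The second reading of the bullet also has support: elsewhere in the same list, *history of* governs a whole series of vascular events. If that reading was intended, most of the gap closes. A safety exclusion that careful readers can take two ways still needs rewording.

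A reader might infer that the protocol gives the site no instruction at all. The documents do not support that. Section 5.2.6 says to withhold CDX-301, Section 5.1.1 gives SBRT to every Arm 1 subject, the calendar still schedules CDX-1140, and Section 4.1 keeps all 46 subjects in the efficacy analyses. The gap is narrower: there is no rule for the regimen of a subject who cannot start CDX-301.

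Two further points stand in part. Section 5.2.6 describes the preclinical evidence as mixed, with exacerbation and improvement both seen; it nevertheless concludes that these patients should not be treated. And Section 5.2.4 says "the CDX-1140 and CDX-301 Investigator Brochures (IB) are the Single Reference Safety Documents". The brochures are not among the documents, so they cannot be used here to settle which section is right. Monitoring after dosing does not answer an instruction not to dose.

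**Conclusion.** The concern holds as a mismatch between the eligibility list and a drug-safety precaution, and it should be corrected. It rests on the more natural reading of the Section 3.2 bullet; on the other reading it shrinks to a difference in wording that is still worth removing.

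Its size can be stated only per patient: a registered patient with past or inactive disease has a 1 in 2 chance of Arm 1. A reader might go further and infer a likely number of affected subjects, or damage to the Phase I safety decision because so few subjects are treated in it. The documents support neither. They give no frequency, and a single subject's share of a small arm says nothing about whether such a subject will be enrolled or will have a DLT. No effect on power, on the type I error rate or on the DLT rule is claimed.

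**What to change.** Reword the Section 3.2 bullet to: *History of allogeneic organ transplant, or active or known history of autoimmune disease.* Check it before randomisation, so that it applies equally to both arms. No separate rule for an Arm 1 regimen without CDX-301 is then needed for this group, because such patients would not be allocated.

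Narrowing Section 5.2.6 to active disease would also remove the mismatch. It would, however, relax a safety precaution on the strength of a brochure that is not in the documents, so it is not proposed here.

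The cost is a one-line amendment and slightly fewer eligible patients, all of them people the protocol already says should not receive CDX-301. The documents do not give the number. Purely as an assumption, if 2% to 10% of otherwise eligible patients had such a history, the loss per 46 would be 46 × 0.02 = 0.92 to 46 × 0.10 = 4.6, or about 1 to 5. That is an upper bound for each assumed rate, since an investigator who already heeds Section 5.2.6 would not register them now.
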